### **1. Background**

Left Atrial Appendage (LAA) Closure (LAAC) is a potent technique of LAA isolation and exclusion for stroke prevention in patients with atrial fibrillation, with evidence from the PROTECT-AF and PREVAIL-AF trials, including their 5-year follow-up assessments, solidifying LAAC as a viable option in these patients with comparable stroke reduction in comparison to oral anticoagulation (OAC) as well as a reduction in bleeding risk, hemorrhagic CVA, and mortality [1-3]. However, the surge in the multiple methods of LAA exclusion has also brought to attention postprocedural complications specific to LAAC, namely, peri-device leaks (PDL) [4]. The stroke implication and classification of PDL itself still lacks consensus, with an increased thromboembolic (TE) potential due to PDL seen in patients with LARIAT and surgical ligation procedures, yet no statistically significant relationship seen in percutaneous and endocardial LAA closure approaches [5-9]. PDL > 5mm has been widely accepted as clinically significant, although there remains limited data with no current established guidelines. [5, 6, 10]. Placement of a septal occluder device such as Amplatzer Vascular Plug, Detachable embolization coils, Gore Cardioform Septal Occluder (CSO; W.L. Gore and Associates, Newark DE), and radiofrequency ablation (RFA) have all emerged as options to resolve residual PDL and post-surgical/ligation leaks [5, 10-12]. However, there exists no head-to-head comparison between these modalities. Given their emergence, we proposed a multi-center observational study to further assess and evaluate these three treatment modalities for their efficacy for leak closure, assessment of pre-, peri- and post-procedural characteristics after leak closure, TE events, and bleeding risk, and complication rates.

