### Inclusion Criteria:

- patients at risk for stroke or thromboembolism that demonstrated any degree of the significant leak on follow up TEE imaging at least 4-6 weeks following either epicardial, endocardial, or surgical LAAC
- Patients undergoing any form of eccentric or centric/central leak closure with available modalities (detachable embolization coils, vascular plug/septal/ASD occluders, or RF Ablation). Criteria for this was made based on the judgement of the operator, with no specific cutoffs for leak size, follow-up time from LAAC to leak closure, etc)
- Age greater than 18 years

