### **Primary Endpoints:**

1. To compare the efficacy of the three PDL closure modalities in patients with prior LAAC

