## **Statistical Analysis:**

Continuous variables will be summarized using mean and standard deviation, while categorical variables will be summarized as counts and percent of the total. Comparison analysis between groups will be made using Kruskal-Wallis tests for nonparametric data sets as appropriate. Leak sizes were measured initially and then via postprocedural follow-up, with overall rates of closure, minimal-mild leaks, and clinically significant leaks listed with associated p-values. All tests were two-tailed, and a  $P$  value less than 0.05 was considered statistically significant. All analyses were performed using SPSS Statistics version 28.0.0.0 (IBM).

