## **Data/Variable Points for Collection:**

- Age
- Sex
- Height
- Weight
- BMI
- Diabetes (y/n)
- Smoking (y/n)
- Dyslipidemia (y/n)
- Prior stroke/TIA (y/n)

- Prior deep venous thrombosis/pulmonary embolism (y/n)
- Ejection Fraction
- History of CAD (y/n)
- Congestive heart failure (y/n)
- Chronic Kidney Disease (y/n)
- Type of Atrial Fibrillation (paroxysmal, persistent, permanent)
- Baseline antithrombotic regimen (aspirin, clopidogrel/prasugrel/ticagrelor, warfarin, direct oral anticoagulant, heparin)
- TIA/stroke after Watchman
- History of major bleeding
- High Fall risk (y/n)
- Previous major bleeding (y/n)
- Previous minor bleeding (y/n)
- Thromboembolism while on oral anticoagulant
- CHA2DS2-VASc Score
- HAS-BLED Score
- Time passed since LAA closure (months)
- Type of LAA Closure (watchman/watchman FLX, amulet, lariat, surgical ligation, atriclip)
- Device Size (if applicable)
- Thrombus on device (y/n)
- Peri-device/central leak size in mm
- Acute success (end of procedure closure) (y/n)
- Procedure duration (minutes)
- Flourosopy time (minutes)
- Contrast usage (mL)
- Hospital length of stay
- Type of procedural anesthesia (general vs light sedation vs local)
- Procedural imaging (TEE, ICE, or both)
- Devices attempted
- Devices deployed
- Combination procedures (combined AF ablation, or LAA occlusion + AF ablation)
- Size/number of devices (plugs/coils)
- Major procedural complications from postoperative day 0-7: stroke, TIA, air embolism, myocardial infarction, cardiac tamponade, device embolization, ventricular tachycardia
- Minor procedural complications from postoperative day 0-7: pericardial effusion
- Complications seen within 90 days of the procedure: cardiovascular death, non-cardiovascular death, stroke/TIA, pericarditis
- Follow-up transesophageal echocardiogram time (months)
- Size of leak at follow up (in mm)
- Follow-up time
- Follow up antithrombotic regimen

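### Modalities are compared on follow-up leak categories without conditioning on entry leak size, so the minimal-mild and clinically significant rates partly reflect which leaks were treated

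*Combined protocol and SAP*

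**What the plan says.** The primary endpoint is "To compare the efficacy of the three PDL closure modalities in patients with prior LAAC". Neither the Objectives nor the Primary Endpoints section says what counts as efficacy at follow-up. The only follow-up efficacy result that the Statistical Analysis section describes is "overall rates of closure, minimal-mild leaks, and clinically significant leaks listed with associated p-values". It gives no mm bounds for these categories and no restriction to, or adjustment for, leak size at entry.

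Entry requires that the patient "demonstrated any degree of the significant leak on follow up TEE imaging at least 4-6 weeks" after LAAC, but the same list leaves the decision to close to the operator, "with no specific cutoffs for leak size, follow-up time from LAAC to leak closure, etc". The word significant has no mm value there. The only size threshold in the document is in the Background: "PDL > 5mm has been widely accepted as clinically significant". The same sentence adds that data are limited and that no guidelines exist.

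The data list includes "Peri-device/central leak size in mm" and the follow-up leak size, also in mm. The only item labelled as a success is closure at the end of the procedure, recorded yes or no.

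**The concern.** The categories describe where a patient ends, not how far the patient moved. With no size limit at entry, some patients may already be in the minimal-mild category before the procedure. If nothing changes, they stay there and are listed as not having a clinically significant leak. They were never at risk of counting against the treatment in that category unless the leak grew.

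This matters for the primary comparison because the design is retrospective and non-randomised. The Objectives describe centres that use different modalities, and the Study Population section leaves the intervention to clinical judgement. Leak size at entry may well differ between coils, plugs or occluders, and RFA. A difference in the category rates, with a p-value attached, could then arise from the mix of leaks treated. A real difference could also be masked.

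**Working it through.** **Plan's own figure.** The only design number is a total of 160 patients. It cannot be reproduced, because no effect size, event rate, power or allocation is given. It is used here only to set a rough group size: 160 / 3 = 53.3, so about 53 per modality if groups are equal (an assumption).

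**Inputs.**
- Bound for clinically significant: over 5 mm, from the Background. The analysis section does not adopt it, so its use is an assumption.
- f, the share entering at or below the bound: not given. Values from 10% to 70% are shown.
- s, the share entering above the bound who end at or below it: not given. Values of 0, 50%, 60% and 80% are shown.
- Small leaks do not grow past the bound (assumption).
- Two-sided test at 0.05, from the Statistical Analysis section.

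**Formula.** Rate free of clinically significant leak = f + (1 - f)s. The clinically significant rate is the complement, (1 - f)(1 - s).

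**Step 1: one modality.** With s = 0 the rate equals f. A procedure that does nothing shows 10%, 30%, 50% or 70% for those values of f.

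**Step 2: same f in both modalities, true s of 60% and 80%.** The reported difference is (1 - f) × 20 points.

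| f | s = 60% | s = 80% | Difference |
|---|---|---|---|
| 10% | 0.10 + 0.90 × 0.60 = 64% | 0.10 + 0.90 × 0.80 = 82% | 18 points |
| 30% | 0.30 + 0.70 × 0.60 = 72% | 0.30 + 0.70 × 0.80 = 86% | 14 points |
| 50% | 0.50 + 0.50 × 0.60 = 80% | 0.50 + 0.50 × 0.80 = 90% | 10 points |
| 70% | 0.70 + 0.30 × 0.60 = 88% | 0.70 + 0.30 × 0.80 = 94% | 6 points |

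**Step 3: different f, same true s.** The last column is the chance of p < 0.05 in a pairwise comparison of two proportions with 53 per group (normal approximation).

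| f, modality A / B | True s in both | Reported A / B | Chance of p < 0.05 |
|---|---|---|---|
| 60% / 20% | 0 | 60% / 20% | 99.3% |
| 60% / 20% | 50% | 80% / 60% | 61.6% |
| 60% / 20% | 80% | 92% / 84% | 24.3% |
| 50% / 25% | 0 | 50% / 25% | 76.5% |
| 50% / 25% | 50% | 75% / 62.5% | 28.2% |
| 50% / 25% | 80% | 90% / 85% | 11.8% |

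With no true difference, the chance should be near 5%.

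**Step 4: different f, different true s.** If A has f = 50% and s = 60%, its rate is 0.50 + 0.50 × 0.60 = 80%. If B has f = 0 and s = 80%, its rate is also 80%. A true 20-point difference disappears.

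**Step 5: what is not affected.** A 4 mm leak that stays at 4 mm is not closed. It fails the closure category whatever its entry size, so unchanged small leaks do not raise the closure rate.

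**The case against.** The strongest reply is that the plan lists three separate rates. It never pools minimal-mild leaks with closure, never names freedom from clinically significant leak as an endpoint, and labels only end-of-procedure closure as a success. A reader might infer that patients with unchanged small leaks are counted as treatment successes. The documents do not support that, and this part of the reply stands. What the plan does do is attach p-values to the minimal-mild and clinically significant rates. Those are affected whether or not anyone calls them success, since the pooled rate in the working is simply one minus the clinically significant rate.

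Second, the 5 mm figure is background, and entry calls for a significant leak. It is therefore not established that a 4 mm leak would be called minimal-mild, or how many such patients entered. This also stands, and it is why the result is conditional and f is shown over a range. It does not remove the problem: any bound applied at follow-up but not at entry has the same effect to the extent that patients enter below it.

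Third, a reader might infer that the flaw always dilutes differences between modalities, for example from 20 points to 10. That holds only if f is the same in every modality, and the 10-point figure also needs f = 50%. At f = 10%, 18 of the 20 points remain. With unequal f the difference can be created, hidden or shrunk.

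Fourth, both leak sizes are recorded in mm, and continuous variables are to be summarised, so a reader may see entry sizes beside the category rates. That helps, but group means do not show which patients moved, and no paired or adjusted comparison is stated.

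**Conclusion.** The concern holds in a limited form. The minimal-mild and clinically significant rates are compared between modalities without regard to entry leak size, although entry has no size cutoff and treatment followed clinical judgement. If over 5 mm is the bound and small leaks do not grow, those rates partly describe who was treated.

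The size cannot be fixed from the documents. It depends on f, on how f differs by modality, and on s, none of which is stated. Under the assumed values, the effect runs from modest (18 of 20 points retained at f = 10% in both modalities) to serious (80% versus 60% with no true difference, and about a 62% chance of a significant p-value).

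The complete-closure rate is not inflated in this way and remains usable. This should be changed, because it bears on the primary comparison and the data to correct it are already being collected.

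**What to change.** In the Statistical Analysis section:

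1. State the mm bounds of the closure, minimal-mild and clinically significant categories, and apply the same bounds at entry and at follow-up.
2. Show, for each modality, a table of entry category by follow-up category, so that an unchanged small leak appears as no change.
3. Report the clinically significant leak outcome among patients who were above that bound at entry.
4. For all patients, compare complete closure and change in leak size in mm between modalities, with adjustment for entry leak size. Adjustment is needed for the change as well, since a small leak has little room to shrink.

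The cost is wording, one table per modality and some analysis work, with no new data. The denominator for the clinically significant outcome becomes smaller: at an assumed f of 50%, about 53 × 0.5 = 26.5, or roughly 27 patients per modality if groups are equal. The rates may also look less favourable.

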## **Data/Variable Points for Collection:**

- Age
- Sex
- Height
- Weight
- BMI
- Diabetes (y/n)
- Smoking (y/n)
- Dyslipidemia (y/n)
- Prior stroke/TIA (y/n)

- Prior deep venous thrombosis/pulmonary embolism (y/n)
- Ejection Fraction
- History of CAD (y/n)
- Congestive heart failure (y/n)
- Chronic Kidney Disease (y/n)
- Type of Atrial Fibrillation (paroxysmal, persistent, permanent)
- Baseline antithrombotic regimen (aspirin, clopidogrel/prasugrel/ticagrelor, warfarin, direct oral anticoagulant, heparin)
- TIA/stroke after Watchman
- History of major bleeding
- High Fall risk (y/n)
- Previous major bleeding (y/n)
- Previous minor bleeding (y/n)
- Thromboembolism while on oral anticoagulant
- CHA2DS2-VASc Score
- HAS-BLED Score
- Time passed since LAA closure (months)
- Type of LAA Closure (watchman/watchman FLX, amulet, lariat, surgical ligation, atriclip)
- Device Size (if applicable)
- Thrombus on device (y/n)
- Peri-device/central leak size in mm
- Acute success (end of procedure closure) (y/n)
- Procedure duration (minutes)
- Flourosopy time (minutes)
- Contrast usage (mL)
- Hospital length of stay
- Type of procedural anesthesia (general vs light sedation vs local)
- Procedural imaging (TEE, ICE, or both)
- Devices attempted
- Devices deployed
- Combination procedures (combined AF ablation, or LAA occlusion + AF ablation)
- Size/number of devices (plugs/coils)
- Major procedural complications from postoperative day 0-7: stroke, TIA, air embolism, myocardial infarction, cardiac tamponade, device embolization, ventricular tachycardia
- Minor procedural complications from postoperative day 0-7: pericardial effusion
- Complications seen within 90 days of the procedure: cardiovascular death, non-cardiovascular death, stroke/TIA, pericarditis
- Follow-up transesophageal echocardiogram time (months)
- Size of leak at follow up (in mm)
- Follow-up time
- Follow up antithrombotic regimen

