## **2. Objectives:**

### Primary Objective:

Our main objective is to collect data from multiple different centers that use different modalities to currently treat either central or peri-device leaks that occur after incomplete LAA closure, and compare each modality in their efficacy and safety outcomes.

Primary Outcome: To compare the efficacy of the three current methods of PDL closure modalities in patients with prior incomplete LAAC.

Secondary Outcome: To compare the rates or reduction of rates of thromboembolic events and procedure-related complications in patients after successful PDL closure with any of the three closure modalities.

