### **Study Population:**

All patients at risk for stroke or thromboembolism that demonstrated any degree of the significant leak on follow up TEE imaging at least 4-6 weeks following either epicardial, endocardial, or surgical LAAC were included in this study population. All patients were evaluated and followed with imaging, and per investigators' respective clinical judgement, then proceeded to have an intervention for leak closure with either detachable embolization coils, vascular plugs/CSO, or RFA.

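### Leak type (central or eccentric peri-device) is a potential confounder of the modality comparison that the plan neither records explicitly nor adjusts for

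*Combined protocol and SAP*

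**What the plan says.** All references are to the combined protocol and SAP.

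- **Scope.** The Primary Objective covers modalities used to "treat either central or peri-device leaks that occur after incomplete LAA closure". The Inclusion Criteria admit "any form of eccentric or centric/central leak closure with available modalities". Both kinds of leak are therefore in the study, and the protocol itself names the distinction.
- **Data items.** Data/Variable Points for Collection has one baseline leak item, "Peri-device/central leak size in mm". The follow-up item, which begins "Size of leak at follow up (in mm", also asks only for a size. The nearest related item is the index procedure, which begins "Type of LAA Closure (watchman/watchman FLX, amulet, lariat, surgical ligation, atriclip".
- **Choice of treatment.** Under Study Population, patients went on to coils, plugs or occluders, or RFA "per investigators' respective clinical judgement". The Inclusion Criteria add: "Criteria for this was made based on the judgement of the operator, with no specific cutoffs for leak size".
- **Analysis.** The Statistical Analysis section names Kruskal-Wallis tests for group comparisons and says closure and residual-leak rates will be listed with p-values. It describes no covariate adjustment, stratification or propensity method for any variable.

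**The concern.** In a retrospective, non-randomised comparison, baseline features of the leak are natural candidates for confounding. They may bear on which modality an operator picks and on whether the leak closes. Leak type is one such feature that the protocol names but does not ask for as a variable. If type is related to both modality and closure, one modality can look better simply because it was used on leaks that close more readily. A real difference could be hidden in the same way.

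A second consequence needs no assumption about confounding. The Primary Endpoints section speaks of PDL closure, while eligibility also takes in central leaks. Without leak type, the investigators cannot report peri-device leaks on their own or show how many central leaks each modality treated.

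**Working it through.** **Step 1. Is leak type recorded?** The combined item gives a unit (mm) and no levels. Elsewhere in the same list, items meant to capture a type say so and give the levels: AF type, index closure type and anaesthesia type all do this. The natural reading of the leak item is one number. The index closure item records how the appendage was closed, not whether the leak was central or eccentric, so it is at best an imperfect proxy.

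**Step 2. Would the planned analysis use it?** No. The Statistical Analysis section adjusts for nothing, including covariates that are collected. A leak-type field alone would not produce an adjusted comparison.

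**Step 3. How large could the bias be?** The plan gives no closure rates, no leak-type shares and no allocation across modalities, and its target of 160 patients has no derivation. There is no plan figure to reproduce. The following is an illustration on assumed inputs.

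Let *p* be closure in peri-device leaks, *c* closure in central leaks, and *s* the share of central leaks in a modality. If modality has no effect, observed closure is *s·c + (1 − s)·p*. The difference between modalities A and B is then

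(s_B − s_A) × (p − c).

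Take p = 85% throughout. The last column is the chance of p < 0.05 in a two-sided test of two proportions with 53 per group (160/3 ≈ 53, equal groups assumed).

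| c | s in A | s in B | Closure A | Closure B | Spurious difference | Chance of p < 0.05 |
|---|---|---|---|---|---|---|
| 85% | 10% | 70% | 85% | 85% | 0 points | about 5% |
| 65% | 20% | 20% | 81% | 81% | 0 points | about 5% |
| 75% | 10% | 50% | 84% | 80% | 4 points | about 8% |
| 65% | 10% | 50% | 83% | 75% | 8 points | about 17% |
| 65% | 10% | 70% | 83% | 71% | 12 points | about 31% |
| 55% | 10% | 70% | 82% | 64% | 18 points | about 55% |

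Worked example for the last row: A = 0.10 × 55 + 0.90 × 85 = 82; B = 0.70 × 55 + 0.30 × 85 = 64; check: (0.70 − 0.10) × (85 − 55) = 18.

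The first two rows show the conditions for no bias: type unrelated to closure, or type unrelated to modality. If central leaks closed more readily than peri-device leaks, the sign would reverse.

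**Step 4. Can type be recovered later?** In principle, yes. The study is retrospective, and eligibility rests on a leak seen on TEE. However, the Informed Consent section has patients de-identified when they are added to the data files, the data storage section calls for early de-identification, and no linkage key is described. Going back may be awkward once a site has finished abstraction.

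**The case against.** The strongest counter-arguments are these.

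- **Leak type is not shown to drive the choice of modality.** A reader might infer that it is a main driver. The documents do not say so. Study Population cites only clinical judgement, and the sentence in the Inclusion Criteria most naturally concerns the decision to close a leak at all. This objection stands: leak type is a plausible confounder, not a demonstrated one.
- **The combined label may already hold the type.** The list is shorthand, not a case report form, and its item on size and number of devices uses a slash for two separate values. A site could enter a peri-device size or a central size. This stands in part: the label allows that reading but does not ask for it, so sites may differ.
- **The information is not lost.** A reader might infer that no later analysis could recover leak type. That goes too far, because the baseline TEE record should allow re-abstraction. What remains is that the dataset as specified does not contain it, and that recovery may be harder after de-identification.
- **The larger gap is the absence of any adjustment.** This is correct. Leak type matters here as a variable the protocol names, does not explicitly collect, and would need for a credible adjusted analysis. The remedy has to cover both the field and the analysis.
- **Post-ligation and surgical leaks are already identifiable** from the index closure item. This stands, so only the central-versus-eccentric split is new.

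**Conclusion.** The point holds as a modest design improvement. Central and eccentric leaks are pooled, type is not an explicit variable, and treatments chosen by judgement are to be compared without adjustment. As specified, the dataset cannot show or correct an imbalance in leak type without a return to source imaging.

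The size is unknown. The range of 0 to about 18 points rests entirely on assumed closure rates and central-leak shares, and the rejection probabilities also assume 53 patients per modality and a pairwise test of proportions. A reader might take one of the middle figures as the expected bias. The documents do not support that, because they give no data on how leak type relates to closure or to modality. The illustration shows only that a material bias is possible and that the plan offers no way to check for it.

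**What to change.** 1. In Data/Variable Points for Collection, replace the combined item with two: baseline leak type (central / eccentric peri-device) and baseline leak size in mm. Use the existing index closure item to identify post-ligation and surgical leaks, not a third level of leak type.
2. Capture the type at first abstraction from the baseline TEE, while sites can still reach the source record. Where abstraction is complete, return to the imaging report.
3. Tabulate leak type by modality before any outcome comparison. If a modality was used almost only on one type, say so and limit the comparison to the type where the modalities overlap.
4. In Statistical Analysis, replace the unadjusted primary comparison with one stratified by or adjusted for leak type, together with baseline leak size and index closure type, both already collected. Unadjusted rates can stay as description.

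The cost is one categorical field from imaging already needed for eligibility, and one more covariate. Precision is the real constraint: two leak types by three modalities make six cells, about 27 patients each if 160 were spread evenly (160/6 ≈ 26.7), and some will be smaller. The model should be kept short, for example by grouping index closure as endocardial, epicardial or surgical.

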### Exclusion Criteria:

- Patients not undergoing leak closure after incomplete LAAC
- Patients unable to complete 45-day follow-up imaging for reevaluation of LAA leak
- Patients unable to consent

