## **Secondary Endpoints:**

1. To compare the reduction/rates of TE events and procedure-related complications (DRT, pericardial effusion/cardiac tamponade, or CVA/TIA) in patients after successful PDL closure with any of the three closure modalities
  - a. Periprocedural complications occurring from Postoperative day #0 – day 7
  - b. Delayed procedure-related complications and adverse events within 90 days of procedure

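### Leak closures combined with AF ablation are eligible and recorded, but the safety comparison by modality neither separates them nor attributes events to a procedure

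*Combined protocol and SAP*

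**What the plan says.** All references are to the combined protocol and SAP.

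- **Eligibility.** Inclusion Criteria admit "Patients undergoing any form of eccentric or centric/central leak closure with available modalities". There are three exclusions: no leak closure, no 45-day imaging, and inability to consent. None concerns a second procedure in the same session.
- **Recording.** Data/Variable Points for Collection lists "Combination procedures (combined AF ablation, or LAA occlusion + AF ablation". Both named forms include AF ablation; the second adds LAA occlusion.
- **Safety endpoint.** Secondary Endpoints compares "procedure-related complications (DRT, pericardial effusion/cardiac tamponade, or CVA/TIA" across the three modalities. The two sub-items are set by timing: "Periprocedural complications occurring from Postoperative day #0" to day 7, and "Delayed procedure-related complications and adverse events within 90 days of procedure". The data list follows the same pattern, for example "Major procedural complications from postoperative day 0-7: stroke, TIA, air embolism, myocardial infarction, cardiac tamponade, device embolization, ventricular tachycardia".
- **Analysis.** Statistical Analysis gives descriptive summaries and then "Comparison analysis between groups will be made using Kruskal-Wallis tests for nonparametric data sets as appropriate". It names no stratum, covariate, restriction or sensitivity analysis.
- **Choice of modality.** Under Study Population, the choice of intervention was left to each investigator's judgement.

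**The concern.** A patient who has leak closure and AF ablation in one session is exposed to the risks of both. Effusion or tamponade and stroke or TIA can come from either. When events are counted by date and compared by leak-closure modality, the modality carries the events of the added ablation as well.

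Comparing the modalities on safety is a stated aim, and the Background says that no head-to-head comparison exists. The result could be read as a ranking of the three techniques. If one modality was more often combined with AF ablation, that ranking would partly reflect how often the second procedure was done. Procedure duration, fluoroscopy time, contrast use and length of stay are exposed to the same mixing, though they are data items and not endpoints.

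**Working it through.** **The plan's own figure.** The only relevant number is the total of 160 patients. The plan states no power, effect size, event rate or split, so it cannot be reproduced. An equal split would give 160 / 3 = 53.3, about 53 per modality; this split is an assumption.

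**Tracing a combined case through the plan.** It meets the inclusion criteria and no exclusion removes it. It is analysed under its leak-closure modality. An event on days 0 to 7 is counted because of its date. No rule says which of the two procedures it belongs to, and no planned analysis uses the combination field. Following the plan as written therefore pools combined and stand-alone cases, although the plan never says so in words.

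**Size, under assumptions.** The documents give none of these inputs:
- c = complication risk of leak closure, the same in both modalities: 2% or 5%
- a = added risk from AF ablation: 2%, 4% or 6%
- f = share of combined cases, modality A vs B: 30% vs 30%, 40% vs 10%, 80% vs 10%, 100% vs 0%

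Treating the two risks as independent, the pooled rate is 1 − (1 − c)(1 − a·f).

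Worked case, c = 2%, a = 4%, shares 80% vs 10%:
- A: 1 − 0.98 × (1 − 0.032) = 5.14%
- B: 1 − 0.98 × (1 − 0.004) = 2.39%
- Risk ratio 2.15, where the true ratio is 1.0
- Part of A's rate due to the added procedure: (5.14 − 2.00) / 5.14 = 61%

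Selected results, with expected events at 53 per modality:

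| c | a | Share A / B | Rate A / B | Risk ratio | Events A / B |
|---|---|---|---|---|---|
| 2% | 4% | 30% / 30% | 3.2% / 3.2% | 1.00 | 1.7 / 1.7 |
| 5% | 2% | 40% / 10% | 5.8% / 5.2% | 1.11 | 3.1 / 2.8 |
| 2% | 4% | 40% / 10% | 3.6% / 2.4% | 1.49 | 1.9 / 1.3 |
| 2% | 4% | 80% / 10% | 5.1% / 2.4% | 2.15 | 2.7 / 1.3 |
| 2% | 6% | 100% / 0% | 7.9% / 2.0% | 3.94 | 4.2 / 1.1 |

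Equal shares leave the comparison unbiased, but both absolute rates are inflated (3.2% instead of 2.0% in the first row). Swapping the shares between A and B inverts the ratio.

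**What the planned tests could show.** Over the whole grid, about 1 to 6 events per modality are expected. At 53 per modality and two-sided alpha 0.05, without adjustment for three pairwise comparisons, power for 2% vs 10% is 41%. The distortion would appear mainly in the point estimates, and the tests could not resolve it.

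**The case against.** Several points against the concern have weight.

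- **The plan never says that cases are pooled.** Its analysis section is a short outline that gives few collected items any role. This is true. But eligibility, grouping by modality and counting by date together produce pooling unless something is added.
- **The endpoint is labelled procedure-related, which could imply a judgement of cause.** With two procedures in one session the label does not say which is meant, and the plan gives no rule.
- **Imbalance is not shown.** A reader might infer that the radiofrequency modality is penalised, because it is itself an ablation and may often accompany AF ablation. The documents give no share for any modality, so this is conjecture. Choice by investigator judgement makes imbalance possible; it establishes neither its presence nor its direction.
- **The effect is small in patients.** In the worked case it is 2.7 vs 1.3 expected events. That is fair, but with so few events a difference of one or two can change the ranking.
- **It is part of a wider gap.** No confounder is adjusted for in this non-randomised comparison. What is distinct here is that an event may belong to a different procedure, and no rule attributes it.

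Two further inferences go too far. A reader might conclude that the leak-closure result, the primary endpoint, needs adjustment for combined procedures; the documents give no mechanism by which AF ablation would change residual leak. A reader might also want stand-alone cases as the main safety population. If 80% of a modality's 53 cases were combined, 53 × 0.2 = 10.6, about 11, would remain. At 2% risk that is 11 × 0.02 = 0.22 expected events, with a 0.98^11 = 80% chance of none. That would nearly empty the comparison.

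**Conclusion.** The concern holds for the secondary safety comparison. As written, the plan counts complications of a same-session AF ablation, with or without LAA occlusion, against the leak-closure modality. The comparison between modalities is biased if combination shares differ. If they are equal it is unbiased, though every rate is inflated.

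Size and direction cannot be determined from the documents. The range of 1.0 to about 3.9 for the spurious risk ratio rests wholly on assumed risks and shares and on independence of the two risks. The upper end needs complete separation of combined and stand-alone cases between two modalities. No stated figure in the plan is wrong, and the primary endpoint is not shown to be affected. A reader might take the data item to cover LAA occlusion alone as an add-on, but both forms it names include AF ablation.

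**What to change.** Add to Statistical Analysis:

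1. Tabulate combined and stand-alone procedures by modality, before any safety comparison.
2. Report procedure-related complications separately for stand-alone and combined procedures within each modality. Do the same, descriptively, for procedure duration, fluoroscopy time, contrast use and length of stay.
3. Keep the full cohort as the main population, and add a stand-alone-only sensitivity analysis of the secondary safety comparison.
4. If a modality has too few stand-alone cases, report the strata descriptively and state that the effect of the modality on safety cannot be separated from that of the added procedure.

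The combination field is already on the data list, so the cost is SAP wording and a few tables. The downside is small strata with few events and wide intervals. The sensitivity analysis will show whether the estimates move, but will seldom settle whether the modalities differ.
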